3.2. Treatments

3.2.1. Treatments Administered

At the beginning of the study, subjects will receive rhPTH[1-84] 25 or 50 µg SC QD in an open-label fashion. Subjects may have their rhPTH[1-84] dose adjusted upwards in increments of 25 µg to a maximum of 100 µg SC QD, with the goal of achieving or maintaining total serum calcium levels in the range of 8.0 to 9.0 mg/dL. The rhPTH[1-84] dose may be adjusted downward at any time as needed to maintain appropriate total serum calcium levels

(approximately 8.0 to 9.0 mg/dL) or due to any safety concerns. rhPTH[1-84] is to be administered into alternating thighs each morning via a multi-dose injection pen device.

3.2.2. Method of Assigning Subjects

Subjects previously enrolled in or who completed the REPLACE or RELAY studies will utilize the same 8-digit subject number that they had been assigned during that study. This number will be utilized to identify the subject throughout the study period. New subjects who were never entered into the REPLACE study will be assigned a new 8-digit subject number.

Subjects will receive study treatment in an open-label fashion at starting doses of rhPTH[1-84] 25 or 50 µg SC QD:

- Subjects with a total serum calcium value of ≤ 9.5 mg/dL will have a starting dose of 50 µg.
- Subjects with a total serum calcium value of > 9.5 mg/dL will have a starting dose as follows:
 - Subjects who are taking supplements (≥ 500 mg oral calcium and/or any calcitriol) will have the supplements reduced or stopped and will start at a dose of 50 µg SC QD.
 - Subjects who are taking minimal or no supplemental calcium (< 500 mg oral calcium) and no calcitriol will have a starting dose of 25 µg SC QD.

The kit number from which cartridges are dispensed to a subject will be recorded on the appropriate eCRF. All subsequent kit numbers will be similarly recorded. All doses of study medication for each subject must be taken from the kit(s) designated for that subject and cartridges from an assigned kit will not be dispensed to any other subject.

3.3. Determination of Sample Size

Approximately 50 subjects are anticipated to be enrolled. This sample size is based on an estimate of the number of subjects who potentially could roll over from RELAY and/or REPLACE study and is not calculated based on the statistical assumptions.

3.4. Changes in the Conduct of the Study or Planned Analyses

3.4.1. Changes in the Conduct of the Study

The SAP is based on Protocol Amendment 6, dated October 24, 2016. Any change of the conduct of the study will be documented in the clinical study report. Any significant changes in the planned analysis will prompt another version of the SAP and therefore a revised SAP.

3.4.2. Changes from Analyses Planned in the Protocol

No changes from protocol specified analyses are planned.

4. Efficacy and Safety Variables

4.1. Schedule of Evaluations and Procedures

All clinical study evaluations will be performed according to [Table 6.1](#), [Table 6.2](#), and [Table 6.3](#). Details of the exact date and time of medical assessments (day/month/year) will be documented in the eCRF. Any deviations from protocol requirements will be documented in the eCRF. A schedule of follow-up visits and procedures for subjects who test positive for PTH-specific antibodies at the last visit is provided in [Table 6.4](#).

Table 4.1 Schedule of Evaluations and Procedures – First 12 Months of Study

Visit Number	1*	Int.	2	3	4	5	6	7	8	9
Study Procedures / Proposed Study Week ^a	BL ^b	1 ^c	4	8	16	24	32	40	48	52
Visit Windows	± 3 days	± 2 days	± 7 days	± 7 days	± 7 days	± 7 days	± 7 days	± 7 days	± 7 days	± 7 days
Informed Consent	X									
Review Inclusion/Exclusion Criteria	X									
Medical History (updated from RELAY/REPLACE)	X									
Concomitant medications (ongoing)	X		X	X	X	X	X	X	X	X
Concomitant medications (new)	X		X	X	X	X	X	X	X	X
Adverse event monitoring (ongoing)	X		X	X	X	X	X	X	X	X
Adverse event monitoring (new)	X		X	X	X	X	X	X	X	X
Assessment of clinical episodes of hypocalcemia and hypercalcemia	X		X	X	X	X	X	X	X	X
Physical examination	X									X
Vital signs ^d and weight	X		X	X	X	X	X	X	X	X
Electrocardiogram (12-lead) (centrally read)	X									X
Bone mineral density by DXA ^e	X									X
Hematology ^f	X									X
Serum chemistry (20-panel) ^f	X									X
Serum calcium (local)**	X	X								
Serum calcium, phosphate, and albumin	X		X	X	X	X	X	X	X	X
Serum calcium, potassium, sodium ^g					X	X	X	X	X	X
Serum 25-hydroxyvitamin D	X		X	X	X	X	X	X	X	X
Serum 1,25-dihydroxyvitamin D						X				X
Serum bone turnover markers	X			X	X	X		X		X
Serum thyroid function test ^{f,h}	X									
Creatinine clearance (estimated GFR)	X				X		X			X
PTH and ECP antibodies ⁱ	X					X		X		X ^l
Serum PTH [1-84] for pharmacokinetic analysis									X ^m	
FSH (newly menopausal women only)	X									
Serum pregnancy test (WOCBP only)	X				X	X	X	X	X	X
Urine pregnancy test (WOCBP only)	X		X	X						
Urinalysis	X									X
24-hour urine calcium, phosphate, sodium, creatinine	X				X		X			X

Visit Number	1*	Int.	2	3	4	5	6	7	8	9
Study Procedures / Proposed Study Week ^a	BL ^b	1 ^c	4	8	16	24	32	40	48	52
Visit Windows	± 3 days	± 2 days	± 7 days	± 7 days	± 7 days	± 7 days	± 7 days	± 7 days	± 7 days	± 7 days
Diary review ^j			X	X	X	X	X	X	X	X
Dispense/administration/accountability of study drug and pen injectors/ancillary supplies	X		X	X	X	X	X	X	X	X
Dispense/accountability of calcium/calcitriol supplements (see guideline)	X		X	X	X	X	X	X	X	X
Dispense subject diaries	X									X
Collect used/unused study drug and supplements ^k			X	X	X	X	X	X	X	X

BL = baseline; DXA = dual-energy x-ray absorptiometry; ECP = *E.coli* protein; FSH = follicle stimulating hormone; GFR = glomerular filtration rate; Int.= interim visit;
PTH = parathyroid hormone; WOCBP = women of child-bearing potential

*Note: Final RELAY study parameters may be used as baseline parameters for this study.

**Any adjustment of study drug or supplemental calcium and calcitriol doses requires testing of total serum calcium concentrations at interim time points.

^a Study visits will be conducted at Weeks 1 (baseline), 4, 8, every 8 weeks thereafter through Week 48, and at Weeks 52.

^b Week 8 from the RELAY study; subjects will return all used/unused drug, supplements, and pens from RELAY/REPLACE.

^c After the End of Treatment visit or early termination visit, subjects who will not continue rhPTH[1-84] treatment will have their total serum calcium and phosphate levels measured 3 to 5 days after the last dose of study medication. Doses of calcium and active vitamin D supplements will be adjusted by the Investigator as appropriate. Thereafter, the Investigator will repeat serum calcium/phosphate monitoring and supplement dose adjustments as appropriate to achieve target serum calcium/phosphate concentrations until the follow up phone call 4 weeks ± 7days after end of treatment visit. After the 4 week follow up phone call, further management of hypoparathyroidism will occur as part of the subject's long-term non-study medical care.

^d Vital signs should be done prior to blood draws.

^e Calcium supplements should be withheld for 24 hours prior to the DXA scan. If a subject cannot withhold the calcium supplements due to safety concern, the DXA should be performed 2 hours after the last calcium tablet has been ingested. Please note: DXA will NOT be completed at baseline if subject had a scan performed within the past 6 months in one of the previous studies (all subjects will have a DXA performed at Week 52 (Visit 9))

^f Fasting for at least 6 to 8 hours prior to test

^g Serum potassium, sodium, and calcium is to be collected 1 week and again 1 month following the institution or change in dose of a calcium-sparing diuretic and then at each subsequent scheduled clinic visit.

^h Thyroid function tests done for final visit of the RELAY/REPLACE studies only.

ⁱ Blood draw for PTH and ECP antibodies will be done predose.

^j A paper diary will be dispensed at baseline for the investigator's use to assess subject's compliance and adherence to the protocol procedures.

^k Subject is to return unused and used cartridges and supplements at each visit.

^l See Protocol Section 6.2 for instructions on follow-up for subjects with PTH-specific antibodies and Table 6-3 for a schedule of follow-up procedures for these subjects.

^m Blood samples for pharmacokinetic analysis will be drawn predose (0 hour) and postdose between 1 and 2 hours and between 6 and 10 hours following study drug administration.

Document: Shire PAR-C10-008 SAP Amendment 1 v2.0 20180322 fix link

Author: PPD

Page 16 of 39

Version Number: 2.0

Version Date: March 22, 2018

Table 4. 2 Schedule of Evaluations and Procedures – Long-term Extension to Month 36

Study Procedures / Proposed Study Month ^{a, b}	Months 14/26	Months 16/28	Months 18/30	Months 20/32	Months 22/34	Months 24/36**
Visit Windows	± 2 weeks	± 2 weeks	± 2 weeks	± 2 weeks	± 2 weeks	± 2 weeks
Concomitant medications	X	X	X	X	X	X
Adverse event monitoring, including pen-related events/complaints	X	X	X	X	X	X
Assessment of clinical episodes of hypocalcemia and hypercalcemia	X	X	X	X	X	X
Physical examination			X ^c			X ^c
Vital signs ^d and weight	X	X	X	X	X	X
Bone mineral density by DXA ^e						X ^f
Hematology ^g						X
Serum chemistry (20-panel) ^g						X
Serum calcium (local)*						
Serum calcium, phosphate	X	X	X	X	X	X
Serum calcium, potassium, sodium ^h	X	X	X	X	X	X
Serum 25-hydroxyvitamin D	X	X	X	X	X	X
Serum 1,25-dihydroxyvitamin D			X			X
Serum bone turnover markers		X		X		X
Creatinine clearance (estimated GFR)		X		X		X
PTH and ECP antibodies ^{i, j}			X			X
Serum pregnancy test (WOCBP only)						
Urine pregnancy test (WOCBP)	X	X	X	X	X	X
Urinalysis						
24-hour urine calcium, phosphate, sodium, creatinine		X		X		X
Diary review ^k	X	X	X	X	X	X
Dispense/administration/accountability of study drug, calcium, and pen injectors/ancillary supplies	X	X	X	X	X	X
Collect used/unused study drug and pen injectors ^l	X	X	X	X	X	X

Document: Shire PAR-C10-008 SAP Amendment 1 v2.0 20180322 fix link

Author: PPD

Version Number:

2.0

Page 17 of 39

Version Date:

March 22, 2018

DXA = dual-energy x-ray absorptiometry; ECP = *E. coli* protein; EoT = end of treatment; F/up = follow up; GFR = glomerular filtration rate; Int.= interim visit; PTH = parathyroid hormone; WOCBP = women of child-bearing potential)

*Any adjustment of study drug or oral calcium and active vitamin D doses requires testing of total serum calcium concentrations at interim time points.

****Following Month 24, the every 2-month visit schedule will repeat (ie, visits procedures for Month 26 are the same as those shown at Month 14.)**

^a Study visits will be conducted every 2 months during the extension portion and will continue until the subject voluntarily withdraws or until termination of the study.

^b After the End of Treatment visit or early termination visit, subjects who will not continue rhPTH[1-84] treatment will have their total serum calcium and phosphate levels measured 3 to 5 days after the last dose of study medication. Doses of calcium and active vitamin D supplements will be adjusted by the Investigator as appropriate. Thereafter, the Investigator will repeat serum calcium/phosphate monitoring and supplement dose adjustments as appropriate to achieve target serum calcium/phosphate concentrations until the follow up phone call 4 weeks \pm 7days after end of treatment visit. After the 4 week follow up phone call, further management of hypoparathyroidism will occur as part of the subject's long-term non-study medical care.

^c Brief physical exams will be conducted at 6-month intervals.

^d Vital signs should be done prior to blood draws.

^e Calcium supplements should be withheld for 24 hours prior to the DXA scan. If a subject cannot withhold the calcium supplements due to safety concern, the DXA should be performed 2 hours after the last calcium tablet has been ingested.

^f DXA will be performed at End of Treatment visit ONLY if the previous DXA was ≥ 3 months prior.

^g Fasting for at least 6 to 8 hours prior to test

^h Serum potassium, sodium, and calcium is to be collected 1 week and again 1 month following the institution or change in dose of a calcium-sparing diuretic and then at each subsequent scheduled clinic visit.

ⁱ Blood draw for PTH and ECP antibodies will be done predose.

^j See Protocol Section 6.4.9 for instructions on follow-up for subjects with PTH-specific antibodies and Table 6-4 for a schedule of follow-up procedures for these subjects.

^k Subjects will record diary information during the 2-week period prior to the next scheduled visit during the long-term extension portion of the study. If the subject does not record the diary information as indicated during this time period, he/she may record it during the 2 weeks following the visit, for review at the next visit or via phone.

^l Subjects are to return unused and used cartridges at each visit. Pens will be collected at the final visit.

Table 4.3 Schedule of Evaluations and Procedures – Long-term Extension after Month 36

Study Procedures	Proposed Study Month ^a	Months 38/50/62	Months 40/52/64	Months 42/54/66	Months 44/56/68	Months 46/58/70	Months 48/60/72	End of Treatment ^b	4 weeks F/up Phone ^c
Visit Windows		± 2 weeks	± 2 weeks	± 2 weeks	± 2 weeks	± 2 weeks	± 2 weeks	± 1 week	± 7 days
Re-consent subject ^d		X							
Concomitant medications		X	X	X	X	X	X	X	
Adverse event monitoring, including pen-related events/complaints		X	X	X	X	X	X	X	X
Assessment of clinical episodes of hypocalcemia and hypercalcemia		X	X	X	X	X	X	X	
Physical examination ^e				X ^e			X ^d	X	
Vital signs ^f and weight		X	X	X	X	X	X	X	
Electrocardiogram (12-lead)								X ^g	
Bone mineral density by DXA ^h							X	X ⁱ	
Hematology ^j							X	X	
Serum chemistry (20-panel) ^j							X	X	
Serum calcium (local)*									
Serum calcium, phosphate		X	X	X	X	X	X	X	
Serum calcium, potassium, sodium ^k		X	X	X	X	X	X	X	
Serum 25-hydroxyvitamin D		X	X	X	X	X	X	X	
Serum 1,25-dihydroxyvitamin D				X			X	X	
Serum bone turnover markers			X		X		X	X	
Creatinine clearance (estimated GFR)			X		X		X	X	
PTH and ECP antibodies ^l				X			X	X ^m	
Serum pregnancy test (WOCBP only)								X	
Urine pregnancy test (WOCBP)		X	X	X	X	X	X		
Urinalysis								X	
24-hour urine calcium, phosphate, sodium, creatinine			X		X		X	X	
Diary review ⁿ		X	X	X	X	X	X	X	
Dispense/administration/accountability of study drug, and pen injectors/ancillary supplies ^o		X	X	X	X	X	X	X	
Collect used/unused study drug / pen injectors ^p		X	X	X	X	X	X	X	

Study Procedures	Proposed Study Month ^a	Months 38/50/62	Months 40/52/64	Months 42/54/66	Months 44/56/68	Months 46/58/70	Months 48/60/72	End of Treatment ^b	4 weeks F/up Phone ^c
	Visit Windows	± 2 weeks	± 2 weeks	± 2 weeks	± 2 weeks	± 2 weeks	± 2 weeks	± 1 week	± 7 days

DXA = dual-energy x-ray absorptiometry; ECP = *E. coli* protein; EoT = end of treatment; F/up = follow up; GFR = glomerular filtration rate; Int.= interim visit; PTH = parathyroid hormone; WOCBP = women of child-bearing potential

NOTE: Following Month 72, the every 2-month visit schedule will repeat (ie, visits procedures for Month 74 will repeat starting with those shown at Months 26/38/50.)

***Any adjustment of study drug or oral calcium and active vitamin D doses requires testing of total serum calcium concentrations at interim time points.**

^a Study visits will be conducted every 2 months and will continue until the subject voluntarily withdraws or until termination of the study (**currently extended at least until December 2016**). At that time, and periodically following the December 2016 milestone, the study will be reviewed in regard to continuation/termination status.

^b After the End of Treatment visit or early termination visit, subjects who will not continue rhPTH[1-84] treatment will have their total serum calcium and phosphate levels measured 3 to 5 days after the last dose of study medication. Doses of calcium and active vitamin D supplements will be adjusted by the Investigator as appropriate. Thereafter, the Investigator will repeat serum calcium/phosphate monitoring and supplement dose adjustments as appropriate to achieve target serum calcium/phosphate concentrations until the follow up phone call 4 weeks ± 7days after end of treatment visit. After the 4 week follow up phone call, further management of hypoparathyroidism will occur as part of the subject's long-term non-study medical care.

^c Follow-up phone contact 4 weeks after the last dose of study medication to check on any ongoing or new drug-related AEs or SAEs

^d Study subjects must be re-consented at their next study visit prior to implementation of Amendment 5.

^e Brief physical exams will be conducted at 6-month intervals.

^f Vital signs should be done prior to blood draws.

^g The End of Treatment ECG will be read locally.

^h Calcium supplements should be withheld for 24 hours prior to the DXA scan. If a subject cannot withhold the calcium supplements due to safety concern, the DXA should be performed 2 hours after the last calcium tablet has been ingested.

ⁱ DXA will be performed at End of Treatment visit ONLY if the previous DXA was ≥3 months prior.

^j Fasting for at least 6 to 8 hours prior to test

^k Serum potassium, sodium, and calcium is to be collected 1 week and again 1 month following the institution or change in dose of a calcium-sparing diuretic and then at each subsequent scheduled clinic visit.

^l Blood draw for PTH and ECP antibodies will be done predose.

^m See Protocol Section 6.4.9 for instructions on follow-up for subjects with PTH-specific antibodies and Table 6-4 for a schedule of follow-up procedures for these subjects.

ⁿ Subjects will record diary information during the 2-week period prior to the next scheduled visit during the long-term extension portion of the study. If the subject does not record the diary information as indicated during this time period, he/she may record it during the 2 weeks following the visit, for review at the next visit or via phone.

^o Ancillary supplies (ie, needles and alcohol wipes) may be supplied, as allowed by local regulations.

^p Subjects are to return unused and used pen injectors at each visit.

Table 4. 4 Schedule of Follow-up Visits and Procedures for Subjects with PTH-specific Antibodies at Final Visit

Follow-up Procedures ^a	Follow-up (Month 3) ^b	Follow-up (Month 6)
Visit Number:	F3	F4
Visit Window (± Days)	±7	±7
Antibodies to PTH	X	X
Adverse events	X	X

AE = adverse event; F = follow-up; PTH = parathyroid hormone

^a Follow-up visits will be conducted for only those subjects who are determined to have PTH-specific antibodies at the end of the End of Study visit (or at the time of discontinuation) and are NOT continuing treatment on commercial Natpara.

^b Subjects who have negative antibody results at Month 3 do not need the Month 6 follow-up visit.

4.2. Efficacy Endpoint

The proportion of subjects in whom the following three conditions are fulfilled at Week 52 (Visit 9) and/or at the End of Treatment will be summarized:

- $A \geq 50\%$ reduction from baseline in dose of oral calcium supplementation or an oral calcium dose of ≤ 500 mg **AND**
- $A \geq 50\%$ reduction from baseline in dose of oral calcitriol supplementation or an oral calcitriol dose of ≤ 0.25 μg **AND**
- An albumin-corrected total serum calcium concentration that is normalized or maintained compared to the baseline value and does not exceed the ULN for the central laboratory

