Wording was clarified for the schedule of follow up visits and procedures for subjects with PTH-specific antibodies at the final 2 visits (rather than the final visit).	Low levels of detectable antibody tend to be variable and of no known clinical significance.	Table 6-3, Table 6-4
Wording was added to clarify that additional interim analyses may be performed as necessary to support regulatory interactions and/or publications.	Updated information.	Section 8.6.3
Removed ( $\geq 7.5$ mg/dL) from the baseline value of albumin-corrected total serum calcium concentration since this was an inadvertent carryover from the previous study, REPLACE. Sentence now reads: An albumin-corrected total serum calcium concentration that is normalized or maintained compared to the baseline value ( <del><math>\geq 7.5</math> mg/dL</del> ) and does not exceed the ULN for the central laboratory	Correction.	Synopsis, Section 2.3.2, Section 8.3

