#### Calcium and Phosphate Regulation

Serum calcium and phosphate levels are regulated principally by parathyroid hormone (PTH), the active vitamin D metabolite 1,25-dihydroxyvitamin D (1,25[OH]2 vitamin D; calcitriol), and calcitonin. PTH maintains an inverse relationship with serum calcium. Normal total serum calcium levels (generally 8.4 to 10.2 mg/dL) and serum phosphate levels (2.5 to 4.5 mg/dL) are regulated to yield a calcium phosphate product of approximately 35 mg/dL. This product is important because of the potential for calcium phosphate salts to be deposited in soft tissues. Levels of the calcium phosphate product that exceed 50 mg/dL are believed to place patients at risk for ectopic soft tissue calcification. PTH is synthesized and secreted by the parathyroid glands primarily in response to a fall in serum calcium levels. Through concerted actions on the kidney and bone, PTH is the principal regulator of plasma calcium homeostasis. In the kidney,

PTH increases renal tubular reabsorption of calcium (while inversely inhibiting phosphate reabsorption) and increases the synthesis of 1,25(OH)2 vitamin D from its precursor 25-hydroxyvitamin D (25[OH] vitamin D). Although 1,25(OH)2 vitamin D has a short in vivo half-life (approximately 6 hours), it directly increases intestinal calcium and phosphate absorption. In bone, PTH increases the efflux of calcium from bone, both from the rapidly exchangeable pool of calcium within bone, and by increasing the number and activity of osteoblasts and osteoclasts, thereby increasing bone turnover. As PTH also acts to inhibit the reabsorption of phosphate in the proximal nephron, it prevents an increase in plasma phosphate levels that could result from increased intestinal phosphate absorption and efflux of phosphate from bone. Calcitonin, secreted by C-cells of the thyroid gland, decreases serum calcium by inhibiting bone resorption and promoting renal tubular calcium excretion, but its effects are relatively minor in comparison to those of PTH and 1,25(OH)2 vitamin D ([Bilezikian et al. 2001](#)).

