### 3 STUDY DESIGN

#### 3.1 Overall Design and Control Methods

This study is a long-term, open-label study using rhPTH[1-84] for the treatment of adult male and female subjects with hypoparathyroidism. The subjects must have previously completed the NPSP558 RELAY study (8 weeks of active therapy) and/or previously completed the NPSP558 REPLACE study (CL1-11-040) (Visit 18).

The goal of this study is to optimize rhPTH[1-84] dosing while reducing calcitriol and oral calcium (carbonate or citrate) supplementation to as low as safely possible while maintaining total serum calcium levels (see [Appendix 2](#), rhPTH[1-84] and Supplement Titration Guideline).

- The starting dose of rhPTH[1-84] for this study will be 25 or 50 µg SC once daily (QD).
- Subjects with a total serum calcium value of  $\leq 9.5$  mg/dL will have a starting dose of 50 µg.
- Subjects with a total serum calcium value of  $> 9.5$  mg/dL will have a starting dose as follows:
  - Subjects who are taking supplements ( $\geq 500$  mg calcium and/or any calcitriol) will have the supplements reduced or stopped and will start at a dose of 50 µg SC QD.
  - Subjects who are taking minimal or no supplemental calcium ( $< 500$  mg) and no calcitriol will have a starting dose of 25 µg SC QD.
- Study visits during the first 12 months of the study will be conducted at Weeks 1 (baseline), 4, 8, and then every 8 weeks thereafter up to Week 48 (Visit 8). The Week 52 visit (Visit 9) is scheduled 4 weeks later.
- At the end of Week 52, subjects will be invited to extend their study drug regimen until January 2018 or after the completion of the last patient's Month 72 visit, whichever comes last. During this time, subjects will return to the clinic for interim visits every 2 months (Months 14, 16, 18, etc).
- All subjects will have their total serum calcium checked by a local laboratory 3 to 5 days ( $\pm 2$  days) following the baseline visit.
- Subjects may have their rhPTH[1-84] dose increased in increments of 25 µg to a maximum of 100 µg SC QD by the investigator at any time during the study, with the goal of achieving or maintaining total serum calcium levels in the range of 8.0 to 9.0 mg/dL. The rhPTH[1-84] dose may be adjusted downward at any time as needed to maintain appropriate serum calcium levels (approximately 8.0 to 9.0 mg/dL) or due to any safety concerns.

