## Appendix 2                      RHPATH[1-84] AND SUPPLEMENT TITRATION GUIDELINE

In this study the goal is to continue rhPTH[1-84] dosing and to reduce calcitriol and oral calcium (carbonate or citrate) supplementation to as low as safely possible, while maintaining total serum calcium levels. In patients with hypoparathyroidism treated with oral calcium and calcitriol, it is suggested to maintain total serum calcium levels in the lower half of the normal range (eg, between 8.0 and 9.0 mg/dL; [Shoback 2008](#)). This is to reduce symptoms and to avoid the hypercalciuria which can occur in the hypoparathyroid patient on calcitriol and oral calcium supplementation ([Horwitz and Stewart 2008](#)). In the current trial, all subjects will receive rhPTH[1-84]. Hence, down-titration of calcitriol and oral calcium must be undertaken, where appropriate, to avoid hypercalcemia. At all times, changes in calcitriol and oral calcium dosing should be undertaken at the discretion of the investigator, based on total serum calcium concentrations and the subject's clinical condition.

To help facilitate a more standardized approach to dose adjustment across study centers, the following guideline has been prepared. The guideline is non-mandatory but the approach suggested should be assessed when adjustments in calcitriol and oral calcium are being considered. In the guideline, all references to total serum calcium levels indicate "predose" (trough) values drawn prior to administration of study drug, rhPTH[1-84] (ie, approximately 23 to 24 hours after the previous injection).

The order and magnitude of subsequent reductions in either calcitriol or oral calcium supplementation is left to the investigator's discretion, based on individual subject response. After any change in the rhPTH[1-84] dose, or a significant change in calcitriol or oral calcium supplement dose, a total serum calcium level **MUST** be measured 3 to 5 days later for safety purposes (unless earlier or more frequent testing is clinically required) and to guide further changes in supplement doses.

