6.7.1. Primary Analysis

As specified in the definition of efficacy endpoint, the subject must meet three conditions at Week 52 and/or EOT to be considered a responder. First, the subject's prescribed daily oral calcium supplementation should be reduced by at least 50% from baseline or an oral calcium dose of ≤ 500 mg; second, the subject's prescribed daily oral calcitriol supplementation dose should be reduced by at least 50% from baseline or an oral calcitriol dose of ≤ 0.25 μg . For the third condition, albumin-corrected total serum calcium concentration should be normalized or maintained compared to the baseline value (≥ 7.5 mg/dL) and does not exceed the ULN for the central laboratory. Different maintenance ranges for this third condition will be assessed in the sensitivity analysis (Section 8.7.5).

The calculation of daily calcium and calcitriol dose is specified in Section 7.4.1. The determination of responders using the subject diary dose data instead of prescribed dose will be used as one of the supportive analyses to the primary analysis.

The number and percentage of responder status will be presented. No formal statistical test will be done. A bar chart for percent of subjects who achieve responder status will be plotted. The percent of subjects who achieve calcium supplement response criterion, and the percent of subjects who achieve calcitriol supplement response criterion will also be plotted in a bar chart.

No statistical testing will be conducted to compare between group differences.

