6.7.5. Sensitivity Analyses

There is no sensitivity analysis planned for this study.

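### Condition 3 of the responder endpoint has two versions in the SAP, leaves *maintained* undefined, and rests on a sensitivity analysis that the SAP both promises and rules out

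*SAP*

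**What the plan says.** SAP 4.2 requires three conditions for response at Week 52 and/or End of Treatment: two on supplement reduction and one on calcium. The calcium condition is "An albumin-corrected total serum calcium concentration that is normalized or maintained compared to the baseline value and does not exceed the ULN", the limit being the central laboratory's. Protocol 2.3.2 and 8.3 use essentially the same words. None of these sections gives a margin, band or lower limit for *maintained*.

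SAP 6.7.1 restates the condition with a number in brackets: "albumin-corrected total serum calcium concentration should be normalized or maintained compared to the baseline value (≥ 7.5 mg/dL"). The Amendment 6 summary of changes took that number out of the protocol because "this was an inadvertent carryover from the previous study, REPLACE". SAP 3.4.1 says the SAP is based on Amendment 6, and SAP 3.4.2 says no changes from the protocol's analyses are planned.

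SAP 6.7.1 continues: "Different maintenance ranges for this third condition will be assessed in the sensitivity analysis", citing Section 8.7.5. The SAP has no such section. Its internal references run two sections high (7.3.2 for 5.3.2, 7.4.1 for 5.4.1), so 6.7.5 is meant. That section reads: "There is no sensitivity analysis planned for this study".

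The rhPTH[1-84] dose is adjusted "with the goal of achieving or maintaining total serum calcium levels in the range of 8.0 to 9.0 mg/dL" (Protocol 3.1). Protocol 1.1 describes "Normal total serum calcium levels (generally 8.4 to 10.2 mg/dL"). Appendix 2 instead speaks of aiming to "maintain total serum calcium levels in the lower half of the normal range (eg, between 8.0 and 9.0 mg/dL").

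**The concern.** The responder proportion is the study's headline efficacy summary and is repeated at every visit. If *maintained* is read as not below baseline, and *normalized* as within a range starting near 8.4 mg/dL, the endpoint and the treatment target pull apart. A subject with a baseline of 8.6 who is held at 8.2 is inside the target, yet is neither normal nor at baseline, and fails. The failure would have nothing to do with supplement reduction. It would also depend on how high calcium was at the REPLACE or RELAY baseline, which SAP 5.3.2 uses for subjects who completed those studies.

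If 7.5 mg/dL is the lower criterion, the same subject passes. Two programmers working from the same SAP could therefore report different responder rates from identical data. The analysis that would show how much the choice matters is the one SAP 6.7.5 says will not be done.

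**Working it through.** The documents state no expected responder rate, power or effect size for this endpoint, so there is no planned figure to reproduce. The check applies the rule directly.

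**Inputs from the documents**
- Titration target: 8.0–9.0 mg/dL (Protocol 3.1).
- General normal range: 8.4–10.2 mg/dL (Protocol 1.1). Appendix 2 places 8.0–9.0 within normal, which would put the lower limit at or below 8.0.
- Figure in SAP 6.7.1: 7.5 mg/dL.
- Planned enrolment: about 50.

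**Assumptions, not in the documents**
- On-target calcium *y* is uniform on 8.0–9.0.
- Baseline *B* is normal with mean 8.5 and SD *s* of 0.5 to 0.8, independent of *y*.
- Titrated total calcium equals albumin-corrected calcium.
- The lower normal limit *L* is varied over 8.0, 8.2, 8.4 and 8.6, because the central-laboratory limit is not given.

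**Share of the target band below normal.** This is (*L* − 8.0)/(9.0 − 8.0): 0% at *L* = 8.0, 20% at 8.2, 40% at 8.4 and 60% at 8.6.

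**Reading A: *maintained* means not below baseline.** An on-target value fails only if *y* < *L* and *y* < *B*. So

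P(fail) = ∫ from 8.0 to *L* of Φ((8.5 − *y*)/*s*) d*y* ≈ (*L* − 8.0) × Φ((8.5 − *m*)/*s*), where *m* is the midpoint of 8.0 and *L*.

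| *L* (mg/dL) | *s* = 0.5 | *s* = 0.8 | On-target subjects failing |
|---|---|---|---|
| 8.0 | 0 | 0 | 0% |
| 8.2 | 0.2 × Φ(0.80) = 0.158 | 0.2 × Φ(0.50) = 0.138 | 14–16% |
| 8.4 | 0.4 × Φ(0.60) = 0.290 | 0.4 × Φ(0.375) = 0.258 | 26–29% |
| 8.6 | 0.6 × Φ(0.40) = 0.393 | 0.6 × Φ(0.25) = 0.359 | 36–39% |

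Exact integration gives the same rounded percentages.

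**Dependence on baseline, at *L* = 8.4.** With one common baseline value, P(fail) = min(*L*, *B*) − 8.0 for *B* of 8.0 or more. That is 0% at a baseline of 8.0 or lower, 20% at 8.2 and 40% at 8.4 or higher. If all 50 subjects were on target, this would be 0, 10 and 20 failures. With baseline uniform on 8.0–9.0, P(fail) = ∫ from 8.0 to 8.4 of (9.0 − *y*) d*y* = 0.40 − 0.08 = 0.32, or 16 of 50.

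**Reading B: 7.5 mg/dL is the floor.** Every on-target value is at least 8.0, so the failure rate on the lower side is 0%.

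**The SAP's own passages compared.** SAP 4.2 has no number and SAP 6.7.1 has 7.5. SAP 6.7.1 says maintenance ranges will be assessed, and SAP 6.7.5 says no sensitivity analysis is planned. These conflicts need no assumption.

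**The case against.** The strongest reply is that SAP 6.7.1 is the operative analysis section and carries 7.5 mg/dL. If that is the floor, no on-target subject fails and the tension with the titration target disappears. That reading has to be shown, and it is why the range starts at 0%. It does not settle the matter. Amendment 6 removed the number, SAP 4.2 omits it, and the sentence leaves unclear whether 7.5 bounds the on-study value or describes the baseline.

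Second, undefined is not the same as zero tolerance. This stands. A reader might infer that on-target subjects are in general scored as failures, or that a subject whose true calcium is unchanged and below normal fails about half the time through measurement noise. The documents support neither as a finding. At a lower limit of 8.4, every value from 8.4 to 9.0 counts as normalized, and lower values fail only if *maintained* means not below baseline and baseline was higher.

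Third, a reader might infer that the maintenance-range analysis was cancelled. The SAP's summary of changes records no such decision; the text simply contradicts itself.

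Fourth, titration uses total calcium, sometimes measured locally, while condition 3 uses albumin-corrected calcium against central-laboratory limits. Treating them as equal is a simplification.

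Finally, the consequences are limited. The primary objective is safety, no formal test is planned, and SAP 6.7.1 plots the calcium and calcitriol supplement criteria separately, so supplement reduction stays visible whatever condition 3 does.

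**Conclusion.** The concern holds as an inconsistency and an undefined term. Condition 3 appears in two versions within the SAP, one of them using a number the governing protocol amendment had withdrawn. *Maintained* has no numeric rule. The analysis meant to explore it is both promised and denied.

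Some on-target subjects can be scored non-responders, but only on one reading. The share ranges from 0% to 36–39% of on-target subjects, depending on that reading and on a central-laboratory lower limit of 8.0 to 8.6 mg/dL; at the protocol's general limit of 8.4 it is 26–29%. These figures rest on the assumed distributions and on equating total with albumin-corrected calcium. What is at stake is an ambiguous, possibly understated descriptive proportion. No error rate or test is affected. The repair should be made because it is cheap and needs no new data.

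**What to change.** 1. Keep the protocol wording as the main definition, and make SAP 4.2 and 6.7.1 agree by removing 7.5 mg/dL from 6.7.1, as Amendment 6 did in the protocol.
2. State in one place the numeric rule for *maintained* and the central-laboratory limits used for *normalized*.
3. Replace the sentence in SAP 6.7.5 with the analysis that 6.7.1 promises, and correct the cross-reference. Give responder tables (a) with *maintained* read as not below baseline, and (b) with a lower analysis limit of 8.0 mg/dL, or the baseline value if baseline was below 8.0. Cap both at the central-laboratory ULN. The limit in (b) is taken from the hypocalcemia text in Protocol Appendix 2. That guideline is non-mandatory, so the limit belongs in a sensitivity table and should not replace the protocol endpoint.
4. Reconcile the descriptions of 8.0–9.0 mg/dL against the normal range in Protocol 1.1 and Appendix 2.

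The limits in step 3 are analysis thresholds only; no change to titration is proposed. The cost is a SAP wording change and one or two extra descriptive tables from data already collected.
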